9.1.1.2. Training/Teaching time required

Other Statistical Analyses
Endpoint(s)

 • Time to read PIL(s) and demonstrate correct inhaler use (T1) • Instruction time by the HCP (including demonstration of correct inhaler use) (T2)
Model Specification

 • The endpoint of training/teaching time will be analysed using the Intent-to-treat population. • This endpoint will be analysed using Kaplan-Meier analysis.
Model Results Presentation

 • Median time to correctly use the inhaler after reading the patient information leaflet (T1) will be presented for each inhaler group. Time will be censored for subjects who did not use the inhaler correctly. Kaplan-Meier survivor functions of T1 will be obtained for each inhaler group and plotted together on the same graph. This analysis will then be repeated with no censoring, only allowing subjects who correctly used the inhaler to be included in the model. • Median time to correctly use the inhaler following HCP's instruction (T2) will be presented for each inhaler group. Time will be set to 0 for subjects who correctly used the inhaler after reading the patient information leaflet, and will be censored for subjects who did not use the inhaler correctly after 3 attempts. Kaplan-Meier survivor functions of T2 will be obtained for each inhaler group and plotted on the same figure. • In all of the above analysis the median time will be taken from the Kaplan Meier model.
SAS Code

 • See Section 8.1.2.4

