To compare the Training/Teaching Time required to demonstrate correct inhaler use	
 • The total amount of time taken to demonstrate correct inhaler use (T1+T2). • The amount of time taken to read the patient information leaflet and demonstrate correct inhaler use (T1) ^d • The amount of time taken to be given instruction by the HCP (up to 2 times) on use of the inhaler and to demonstrate correct inhaler use (T2) ^d
Preference attributes for each treatment option tested ^b	Treatment preference, from questionnaire for: 
 • Number of steps required to take COPD medication • Over all treatment preference
a. Over all and critical errors for each inhaler tested, as well as an explanation of how these endpoints were defined, are listed in Appendix 2 b. Preference Questionnaires for each sub-study are included in Appendix 3 c. To show correct inhaler use a subject demonstrates the use of the inhaler without making any critical or non-critical error d. Endpoint will be treated as 'other endpoint' and not secondary for the statistical analysis	

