9.1.1.3. Time Taken to Use Device

Time taken to use the device will be recorded as follows:

- T1: the time from when the subject starts to read the patient instruction leaflet until they have completed demonstration of device use (i.e., with no investigator support).
- T2: the time from when the HCP starts to instruct subject until correct use is demonstrated (up to a maximum of two attempts only).
- T1+T2: the time from when the subject starts to read the patient information leaflet until correct use is demonstrated (up to a maximum of three attempts, once after reading the PIL and following instruction, up to 2 times, by HCP).

The HCP will start recording (clock start) the time from when T1 begins and will stop when device use has been demonstrated. The clock re-starts when T2 begins and stops once correct use has been demonstrated, or when three failed attempts have been made. Note: T2 includes the time used by the investigator for re-instructing the Subjects throughout.

For subjects who demonstrate correct inhaler use after reading the PIL, T2 will be 0.

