10.4. Statistical Analyses

10.4.1. Efficacy Analyses

Endpoint	Statistical Analysis Methods
Primary	
The primary endpoint is the percentage of subjects making at least one critical error after reading the PIL(s).
 
This endpoint will be analysed using conditional logistic regression with subject as fixed strata, and treatment option and period as fixed effects. The odds ratio, 95% CI and p-value will be presented for the comparison between treatment options. It will be based on a two-sided hypothesis testing approach of superiority.

Secondary	
The following endpoints will be analysed in the same way as for the primary endpoint if there are sufficient subjects making errors otherwise the data will be summarised only:
 
 The percentage of subjects making at least one critical error after the first instruction from the HCP The percentage of subjects making at least one overall error after reading the PIL(s) The percentage of subjects making at least one overall error after the first instruction from the HCP 
The number of instructions (0, 1 or 2 times) from the HCP which are needed to demonstrate correct inhaler use will be analysed using the Wilcoxon signed rank test.
 
The total amount of time taken to demonstrate correct inhaler use (T1+T2)

Endpoint	Statistical Analysis Methods
	
will be analysed using Kaplan-Meier methods.
 
Treatment preference from questionnaire will be analysed using a Cochran-Mantel-Haenszel test, adjusted for study inhaler use sequence.

Other	
Analysis of the following other endpoints will be defined in the Reporting and Analysis Plan.
 
 • The percentage of subjects making at least one critical error after the second instruction from the HCP • The percentage of subjects making at least one overall error after the second instruction from the HCP • The amount of time taken to read the patient information leaflet and demonstrate correct inhaler device use (T1) • The amount of time taken to be given instruction by the HCP on use of the inhaler and demonstrate correct inhaler use (T2)

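### The SAP censors T1 for subjects who make an error, although their first attempt is finished and timed, so the Kaplan-Meier median mixes error rate with time; the repeat in correct users only does not repair this

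*SAP*

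**What the plan says.** The documents describe T1 in two ways.

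- **Timing rule (Protocol 9.1.1.3).** "T1: the time from when the subject starts to read the patient instruction leaflet until they have completed demonstration of device use". The clock instruction agrees: "The HCP will start recording (clock start) the time from when T1 begins and will stop when device use has been demonstrated". Correct use appears as a stopping condition for T2 and for the total, not for T1. The schedule of activities also omits the word correct for this time.
- **Endpoint name (Protocol Section 4).** "The amount of time taken to read the patient information leaflet and demonstrate correct inhaler use (T1". Protocol 10.4.1 uses nearly the same words and leaves the analysis to the SAP. SAP 2.2 and 9.1.1.2 keep the word correct. A note to Section 4 defines correct use as no critical and no non-critical error.

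SAP 9.1.1.2 then plans two Kaplan-Meier analyses. In one, "Time will be censored for subjects who did not use the inhaler correctly". Of the other it says: "This analysis will then be repeated with no censoring, only allowing subjects who correctly used the inhaler to be included in the model". Under the footnote to shell EFF_T02 (SAP Appendix 12), an error on either inhaler of a two-inhaler option censors the summed time.

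On the status of T1, a note to Protocol Section 4 reads: "Endpoint will be treated as 'other endpoint' and not secondary for the statistical analysis".

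**The concern.** Censoring is meant for a subject whose event may still occur after observation stops. Here the subject has read the leaflet, finished the demonstration and been timed. What follows is instruction by the healthcare professional, on a separate clock (T2). Nothing about T1 remains unknown.

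What triggers censoring is an error, and error rates are what the trial expects to differ between options. A difference in errors can therefore appear as a difference in time, and the same subjects' errors are already reported under their own endpoints. Restricting to correct users removes the censoring but conditions on an outcome of the device, so the two options are described in different, self-selected sets of subjects. A reader could be given two T1 results that disagree, with no rule for choosing between them.

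**Working it through.** The plan gives no expected T1, spread, share correct or test for T1, so there is no figure to reproduce. The check is what the planned rules return when both options have the same true T1 distribution.

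**Inputs from the documents**
- 72 evaluable subjects per sub-study (Protocol 10.2).
- Planning row of 10% critical errors on ELLIPTA and at least 35% on the comparator (Protocol 10.2). The share fully correct, p, is then at most 0.90 and at most 0.65, because non-critical errors also count as incorrect.

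**Assumed:** T1 lognormal, with median m and log SD σ as stated below.

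**Step 1: what censored Kaplan-Meier estimates.** Let S(t) be the survivor function of real T1, with hazard h(t). If a share p is correct regardless of time, the hazard of a correct completion is p·h(t). The remainder are censored at their own completed T1, so

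S_KM(t) = exp(−∫p·h) = S(t)^p.

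The Kaplan-Meier median is where S(t)^p = 0.5. It therefore sits at percentile 1 − 0.5^(1/p) of real T1, whatever the time distribution.

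| Critical errors (planning row) | p, ELLIPTA v comparator (upper limits) | Percentile of real T1 reported as the median |
|---|---|---|
| 11% v 37% | 0.89 v 0.63 | 54.1 v 66.7 |
| 10% v 35% | 0.90 v 0.65 | 53.7 v 65.6 |
| 6% v 29% | 0.94 v 0.71 | 52.2 v 62.3 |

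For the middle row: 1 − 0.5^(1/0.90) = 0.537 and 1 − 0.5^(1/0.65) = 0.656.

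**Step 2: in minutes.** The normal quantiles at 0.537 and 0.656 are about 0.093 and 0.401, so the false gap is m·[exp(0.401σ) − exp(0.093σ)].
- m = 4, σ = 0.4: 4.15 v 4.70 min, gap about 0.5.
- m = 5, σ = 0.5: 5.24 v 6.11 min, gap about 0.9.
- m = 3, σ = 0.3: 3 × (1.128 − 1.028), gap about 0.3.

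Uncensored, the two medians are equal in every case.

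**Step 3: correctness linked to time.** These figures are from simulation (200,000 subjects, m = 4, σ = 0.4, p = 0.90 v 0.65), with an assumed change in the log-odds of being correct per SD of log time. The true median is 4.0 min for both options.

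| Assumed link | Censored Kaplan-Meier | Correct users only |
|---|---|---|
| Slower subjects less often correct (−1) | 4.06 v 4.42 | 3.87 v 3.57 |
| No link (0) | 4.15 v 4.70 | 3.99 v 4.01 |
| Slower subjects more often correct (+1) | 4.22 v 4.85 | 4.14 v 4.48 |

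In all three cases the censored analysis makes the option with more errors look slower. The correct-users-only result has no bias with no link, and otherwise goes in either direction.

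**Step 4: who remains in the repeat.** 72 × 0.90 ≈ 65 ELLIPTA subjects and 72 × 0.65 ≈ 47 comparator subjects. Between 72 × (0.90 + 0.65 − 1) ≈ 40 and 47 subjects are in both sets.

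**The case against.** The best defence is that the SAP follows the endpoint's name. Protocol Section 4 and 10.4.1 both say correct use, Protocol 10.4.1 defers the method to the SAP, and the SAP labels its result as a median time to correct use. That stands in part. A reader might infer that the protocol plainly defines T1 as fully observed and that the SAP simply contradicts it. The documents do not support that, because the conflict is already inside the protocol. The name does not rescue the method, however. On a clock that stops at the end of the first demonstration, a subject who failed cannot become correct later, so censoring is wrong for time to correct use as well.

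A reader might also infer that no uncensored T1 will be seen. SAP 9.1.1 plans separate summary statistics for T1, shell EFF_T02 has n, mean, SD, median, minimum and maximum above the Kaplan-Meier median, and a listing gives each subject's time. This objection stands, with one gap: the SAP does not say whether that n includes incorrect users.

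Extreme distortions should not be claimed. At 40% correct the median would be the 82nd percentile. But EFF_T02 suppresses the Kaplan-Meier median once over half the times are censored, and at n = 72 that happens with probability 95% at 40% correct, 45% at 50% and 0.3% at 65%.

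Nor can it be said that the correct-users-only repeat hides or reverses a difference, since its direction depends on an unknown link between speed and correctness. It is also not the sole cause of lost pairing: the planned Kaplan-Meier code stratifies by treatment and has no subject term.

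**Conclusion.** The point holds in this form. The two descriptions of T1 need reconciling, and neither planned Kaplan-Meier analysis gives a sound comparison between options. The percentile shift in the censored analysis, about the 54th v the 66th at the 10% v 35% row, needs no assumption about the shape of the time distribution. It does assume that correctness is unrelated to time and that the shares correct are at their upper limits. The 0.5 to 0.9 min rests on assumed times (medians of 4 to 5 min, log SD 0.4 to 0.5) and is smaller for shorter or less variable times. For the repeat, the problem is selection of unknown direction.

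A reader might infer that the trial's conclusions are at risk. They are not: T1 is an 'other' endpoint, and its shell shows neither a p-value nor a between-option estimate. It still merits correction, because training time is in the study title and SAP Table 5 marks T1 for formal statistical analysis.

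**What to change.** - Use one definition of T1 throughout. If the timing rule in Protocol 9.1.1.3 governs, align the endpoint name in Protocol Section 4 and 10.4.1 and in SAP 2.2 and 9.1.1.2, and record the change in SAP 2.1.
- Make the main T1 result the recorded time, uncensored, for all ITT subjects who complete both periods. Sum it over the two inhalers for the combination and report within-subject differences.
- State that n in EFF_T02 includes incorrect users, and show the percentage correct after the leaflet beside the times.
- If time to correct use is also wanted, plot a cumulative proportion correct in which failures stay in the denominator and the curve levels off at the share correct, instead of the censored Kaplan-Meier curve.
- Drop the correct-users-only repeat, or label it descriptive.

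The cost is SAP wording, a clarification of the protocol's endpoint name and simpler code. No new data are needed. T1 would no longer carry information on correctness, but the error endpoints already report that.

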9.2. Safety Analyses

9.2.1. Overview of Planned Safety Analyses

These other safety analyses will be based on the ITT populations, unless otherwise specified.

[Table 6](#) provides an overview of the planned safety analyses, with further details of data displays being presented in [Appendix 11](#): List of Data Displays.

Table 6 Overview of Other Planned Safety Analyses

Endpoint	Absolute	
	Summary	Individual
	T	L
Adverse Events		
Overview of AEs	Y	
On-treatment AEs, drug related AE's, fatal/non-fatal SAE's, fatal/non-fatal drug related SAE's	Y	Y
Summary of Serious Adverse Events by System Organ Class and Preferred Term (Number of Subjects and Occurrences)	Y	
On-treatment serious AEs experienced by 3% (before rounding) or more of subjects in any treatment group	Y	
On-treatment non-serious AEs experienced by 3% (before rounding) or more of subjects in any treatment group	Y	
Subject numbers for individual AEs (ASE)		Y
All AEs including identification of whether each AE occurred pre-treatment or on-treatment (ASE)		Y
Non-fatal SAEs (ASE)		Y
Fatal AEs (ASE)		Y
On-treatment drug related SAEs		Y
AEs leading to discontinuation of study treatment or withdrawal from the study	Y	Y
Cardiovascular Events		Y
Relationship between adverse event system organ class, preferred term and verbatim text (ASE)		Y

NOTES :

- T = Table, L = Listing, Y = Yes display generated.
- Summary = Represents TL related to any summaries (i.e. descriptive statistics) of the observed raw data.
- Individual = Represents TL related to any displays of individual subject observed raw data.

9.2.1.1. Adverse Events and Serious Adverse Events

A summary of the following AEs and SAEs will be provided:

- Any AE (pre treatment -, on- treatment or post-treatment)
- Any on-treatment drug related AE
- Any AE (pre-treatment or on-treatment) leading to permanent discontinuation of study treatment or withdrawal from study
- Any non-fatal SAE
- Any fatal SAE
- Any on-treatment non-fatal drug related SAE
- Any on-treatment fatal drug related SAE

AE incidence will be summarised overall using the primary System Organ Class (SOC) and preferred term. All listings of AEs/SAEs will identify whether each adverse event occurred during screening, on treatment or after treatment.

9.2.1.2. Cardiovascular Events

For subjects who report a cardiovascular event, individual patient profiles will be produced for one or more of the following categories:

- Myocardial infarction/unstable angina
- Congestive heart failure
- Arrhythmias
- Valvulopathy
- Pulmonary hypertension
- Cerebrovascular events/stroke and transient ischemic attack
- Peripheral arterial thrombosis
- Deep Venous Thrombosis
- Revascularization

9.2.2. Pregnancies

Any pregnancies reported during the study will be summarised in case narratives. Any pregnancy complication or elective termination of a pregnancy for medical reasons will be recorded as an AE or SAE and included in summaries and listings of AEs/SAEs.

11. APPENDICES

Section	Appendix
RAP Section 4 : Analysis Populations	
Section 11.1	Appendix 1: Protocol Deviation Management
RAP Section 5 : General Considerations for Data Analyses & Data Handling Conventions	
Section 11.2	Appendix 2: Time & Events
Section 11.3	Appendix 3: Treatment Phases
Section 11.4	Appendix 4: Data Display Standards & Handling Conventions
Section 11.5	Appendix 5: Derived and Transformed Data
Section 11.6	Appendix 6: Premature Withdrawals & Handling of Missing Data 
 • Premature Withdrawals • Handling of Missing Data
Section 11.7	Appendix 7: Multicenter Studies
Section 11.8	Appendix 8: Examination of Covariates, Subgroups & Other Strata
Section 11.9	Appendix 9: Model Checking and Diagnostics for Statistical Analyses
Other RAP Appendices	
Section 11.10	Appendix 10: Abbreviations & Trade Marks
Section 11.11	Appendix 11: List of Data Displays
Section 11.12	Appendix 12: Example Mock Shells for Data Displays

11.1. Appendix 1: Protocol Deviation Management

The full list of protocol deviations collected on the eCRF is in the Protocol Deviation Management Plan (PDMP). Please refer to this document for current guidance.

11.2. Appendix 2: Time & Events

11.2.1. Protocol Defined Time & Events

Visit Number	V0	V1	Notes
Study Day	1	1	V0 can take place on the same day as V1. V1 should be completed no later than 30 days after consent.
Procedure:			
Screening Assessments			Completed prior to randomisation
Written informed consent	X		Informed consent may take place prior to V0 for logistical reasons. Subjects should be included and randomised within 30 days of providing consent.
Subject demography	X		Age, height, weight, year of birth, sex, ethnicity and geographic ancestry will be recorded
Medical/disease history including Chronic Obstructive Pulmonary Disease (COPD)	X		Subject will have a medical history of COPD, previously confirmed by spirometry.
Concomitant medication history including COPD Therapy History	X		Current concomitant medication will be recorded. A minimum COPD therapy history for the preceding 2 years from inclusion will be recorded
Inclusion/exclusion criteria	X		All criteria must be met prior to randomisation at V1
Study Assessments			Completed once a subject is included on study
Randomisation		X	Randomised to treatment order and preference questionnaire
Assess the number of inhaler errors (critical and overall) on each treatment after reading the Patient information leaflet (PIL) for Inhaler tested		X	No instruction is provided by the Health Care Professional (HCP) for this assessment.
Assess the number of inhaler errors (overall and critical) on each treatment after each of 2 attempts following instruction by HCP		X	If a subject cannot show correct use after reading the PIL, then the HCP has up to 2 attempts to instruct the subject to attain this.

Visit Number	V0	V1	Notes
Teaching-Training Time for each inhaler includes the following: 
 • The amount of time taken to read the patient information leaflet and demonstrate inhaler use • The amount of time taken to be given instruction by the HCP on use of the inhaler and demonstrate inhaler use • The total amount of time taken to demonstrate inhaler use 		X	
 • First assessment is attempt one, including time to read PIL and demonstrate use. • Second assessment will be time for HCP to correct errors and subject to show use for up to 2 more attempts • The Cumulative time for all assessments needed by subject and any HCP instruction to demonstrate no errors will also be captured.
Preference Questionnaire		X	Subject will complete version of Preference Questionnaire they have been randomised to.
SAE/AE assessment		X	Collected until completion of final study assessment at V1.

11.3. Appendix 3: Treatment Phases

11.3.1. Treatment Phases

All data if necessary will be categorised according to the following treatment phases; pre-study, during- study and post- study. These definitions will be defined based on the date of Visit 1, as this is the visit where subjects complete all study assessments. In addition, as date and not time is captured in the eCRF the treatment phase can only be applied if an event spans multiple days.

11.3.2. Treatment Phase Definitions

Definition	Treatment Phase		
	Pre-study	During-study	Post-study
Before Visit 1	Y		
At Visit 1		Y	
After Visit 1			Y

11.4. Appendix 4: Data Display Standards & Handling Conventions

11.4.1. Study Treatment & Sub-group Display Descriptors

Treatment Group Descriptions			
RandAll NG		Data Displays for Reporting	
Code	Description	Description	Order ^[1]
A	ELLIPTA Inhaler	ELLIPTA	1
B	DISKUS Inhaler + HandiHaler Inhaler	DISKUS + HandiHaler	2
C	Turbuhaler Inhaler + HandiHaler Inhaler	Turbuhaler + HandiHaler	3
Q1	Preference Questionnaire 1	Q1	4
Q2	Preference Questionnaire 2	Q2	5
Q3	Preference Questionnaire 3	Q3	6
Q4	Preference Questionnaire 4	Q4	7

NOTES:

1. Order represents treatments being presented in TFL, as appropriate.

11.4.2. Reporting Process & Standards

Reporting Process	
Software	

 The currently supported versions of SAS software will be used. The currently supported versions of TSCG software will be used. 	
Reporting Area	
HARP Server	: uk1salx00175
HARP Area	/arenv/arprod/gsk2834425/mid206215/final_01
QC Spreadsheet	/arenv/arwork/gsk2834425/mid206215/final_01/documents
Analysis Datasets	

 Analysis datasets will be created according to Legacy GSK A&R dataset standards. 	
Generation of RTF Files	

 RTF files will be generated for use in writing the CSR. 	

Reporting Standards	
General	

 • The current GSK Integrated Data Standards Library (IDSL) will be applied for reporting, unless otherwise stated: 
 ○ 4.03 to 4.23: General Principles ○ 5.01 to 5.08: Principles Related to Data Listings ○ 6.01 to 6.11: Principles Related to Summary Tables ○ 7.01 to 7.13: Principles Related to Graphics 	
Formats	

 • All data will be reported according to the actual treatment option the subject received unless otherwise stated. • GSK IDSL Statistical Principles (5.03 & 6.06.3) for decimal places (DP's) will be adopted for reporting of data based on the raw data collected. • Numeric data on listings will be reported at the precision collected on the eCRF. 	
Planned and Actual Time	

 • Reporting for Data Listings: 
 • Unscheduled or unplanned readings will be presented within the subject's listings but not presented in summary tables. 	
Descriptive Summary Statistics	
Continuous Data	Refer to IDSL Statistical Principle 6.06.1
Categorical Data	N, n, frequency, %
Graphical Displays	

 • Refer to IDSL Statistical Principals 7.01 to 7.13. 	

